5.2 Safety Endpoints/Variables

5.2.1 Primary Safety Endpoint

[figure not shown]
No primary safety endpoint has been defined.

5.2.2 Secondary Safety Endpoints

- Incidence of related treatment-emergent adverse events (TEAEs) in MP.

- Incidence of related TEAEs in OLEX period

For the definition of TEAEs, see CCI

CCI

6 Statistical Analysis Methods

Continuous endpoints (values and changes from baseline/ cycle baseline, where applicable) will be summarized by number of subjects in the respective analysis set/ population (N), number of values analyzed (n), mean, standard deviation, median, quartiles, minimum, and maximum. If relevant, the number of values imputed due to missingness (nimp) will be reported for efficacy variables (see [Section 6.4.1](#)). Mean, quartiles, and median will be reported to one decimal place more than the data were collected, for the standard deviation two decimal places more will be displayed; for derived data, an adequate number of decimal places will be chosen.

For qualitative endpoints, absolute and percent frequencies (n, %) and, if applicable, shift tables will be displayed. Frequency tables will include the number of missing values, if applicable. Percentages will be calculated using the denominator of all subjects in a specified population or treatment group. The denominator will be specified in a footnote to the tables for clarification if not otherwise obvious. Percentages will be reported to one decimal place. In frequency tables based on observed cases, number of missing values will not be presented and percentages will be based on number of observed cases (Nobs).

If not otherwise specified, statistical tests will be conducted two-sided at type I error rate 5%. P-values will be reported to four decimal places (e.g., $p=0.0375$). P-values below 0.0001 will be presented as '<0.0001'. Confidence intervals (CIs) will be two-sided 95%.

In general, values obtained at Visit 2 are defined as the baseline values. Where data is not recorded at Visit 2, the last measurement before start of treatment is defined as baseline value. These values will be analyzed as baseline (i.e. baseline flag is 'yes' for last record with non-missing value before first treatment in Study Data Tabulation Model [SDTM]). For cycle 2 values obtained at Visit 8 and for cycle 3 values obtained at Visit 13 will be used as cycle baselines.

6.1 Efficacy Endpoints and Efficacy Estimands

Primary and sensitivity analyses of primary efficacy endpoints (see [Section 6.1.1.1](#)) and confirmatory analyses of key secondary endpoints will be based on the target population of main primary and key secondary efficacy estimands (see [Section 5.1.1](#) and [Section 5.1.2](#), respectively). It is defined as "Male and female adults (18 years of age or older) with HFL, GFL, and LCL of moderate (score of 2) to severe (score of 3) intensity at maximum contraction as assessed by the investigator and the subject according to MAS, as randomized in this study: Subset of subjects randomized to UFL treatment group or to Placebo treatment group, grouped by randomized treatment assignment.". Further efficacy analyses will be based on the FAS if not otherwise specified. Statistical tests will be two-sided hypothesis tests for between treatment differences in general. Adequate descriptive statistics as specified at the beginning of [Section 6](#) above will be provided for all endpoints.

In case Visit 7/Visit 8 or Visit 12/Visit 13 is performed on same day MAS assessments from Visit 7/Visit 12 will be duplicated to be also analysed and listed at Visit 8/Visit 13.

[figure not shown]
6.1.1 Primary Efficacy Endpoints and Estimands

The primary endpoints will be proportions of GFL-, HFL- and LCL-responders as defined in [Section 5.1.1](#). These proportions will be compared for treatment groups U and P. It should be noted that Group G&H is not part of the primary efficacy analysis which has the objective to compare efficacy of simultaneous treatment of UFL with NT 201 versus placebo. Group G&H and Total NT 201 (Group U and Group G&H pooled) will be considered in the supplementary analyses of primary endpoints on the FAS, the PPS, observed cases in the FAS, observed cases in the PPS (see below), in supplementary analyses of key secondary endpoints, and in analyses of further secondary and other efficacy endpoints.

The three main primary efficacy estimands are defined in [Section 5.1.1](#) (see CCI for GFL, CCI for HFL, CCI for LCL).

[figure not shown]
6.1.1.1 Primary analysis

The following main estimators for main primary estimands will serve as primary analysis: For comparison of proportion of GFL-, HFL- and LCL-responders in treatment groups U and P, Mantel-Haenszel stratum weights and the Sato variance estimator will be used to calculate the stratum-adjusted risk difference, with study site serving as stratum variable. For each anatomical region, the stratum-adjusted (common) difference in response rates between treatment Group U and Group P (reference) (“Group U” – “Group P”) will be provided with two-sided p-value and 95% Mantel-Haenszel confidence interval (CI). The null hypothesis of the Mantel-Haenszel test is that the common difference in response rates is zero. The family-wise two-sided type I error level $\alpha = 0.05$ will be controlled by a hierarchical test procedure based on two-sided tests with $\alpha = 0.05$ as described in [Section 6.4.3](#).

Strategies for handling of ICEs are described in [Section 6.4.6](#).

Missing data will be imputed so that all subjects in the target population of main primary estimands can be included in the analysis. CCI

[figure not shown]

CCI

Responder rates with two-sided 95% Wilson CIs will be provided as well for both treatment groups included in target population of main primary efficacy estimands, overall and per study site.

¹ In the CSP, it was erroneously stated that the score from V3 (Day 8) is likely lower than the score to be expected at Day 30. This is no change to planned analyses since no change to the imputation rule is implied. Only the justification for imputing monotonously missing data at V4, V5, V6, and V7 with V3 data (conservative approach) was corrected.

A similar SAS code to the following statements will be employed for this analysis (example for comparison of GFL responders):

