NT 201 (active ingredient: NT 101, BoNT type A [BoNT-A], free from complexing proteins, US Adopted Name incobotulinumtoxinA) or matching placebo provided in 100 U vials.

CCI

Statistical analysis methods

Adequate descriptive statistics will be provided for each efficacy endpoint and timepoint. Primary and sensitivity analyses for primary efficacy endpoints will be based on the target population of main primary estimands which is defined as “Male and female adults (18 years of age or older) with HFL, GFL, and LCL of moderate (score of 2) to severe (score of 3) intensity at maximum contraction as assessed by the investigator and the subject according to MAS, as randomized in this study: Subset of subjects randomized to UFL treatment group or to Placebo treatment group, grouped by randomized treatment assignment.” Further efficacy analyses will be based on the full analysis set (FAS) including all randomized subjects, if not otherwise specified.

The primary analysis of primary endpoints will be comparison of proportion of GFL-, HFL- and LCL-responders in treatment groups U and P by Mantel-Haenszel tests of the null hypothesis that the stratum-adjusted difference in response rates at Day 30 is zero, with study site serving as stratum variable.

The family-wise two-sided type I error level $\alpha = 0.05$ will be controlled by a hierarchical test procedure based on two-sided tests with $\alpha = 0.05$. First, a test for superiority of U

CONFIDENTIAL

CCI

versus P will be conducted for proportion of GFL-responders, then for proportion of HFL-responders and finally for proportion of LCL-responders. The test procedure will stop once statistical significance could not be reached.

Group G&H will not be part of the primary efficacy analysis.

All safety analyses will be performed on the SES.

Listings and tables displaying incidences of related TEAEs in MP and OLEX will be provided by Medical Dictionary for Regulatory Activities (MedDRA) system organ class and preferred term by randomized study group and overall, for the total study period and by treatment cycle. For the analyses by treatment cycle, the denominator for the incidences will be adjusted to all subjects being treated in that treatment cycle.

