For comparison of proportion of GFL-, HFL- and LCL-responders in treatment groups U and P, Mantel-Haenszel stratum weights and the Sato variance estimator will be used to calculate the stratum-adjusted risk difference, with study site serving as stratum variable. For each anatomical region, the stratum-adjusted (common) difference in response rates between treatment Group U and Group P (reference) will be provided with two-sided p-value and 95% Mantel-Haenszel confidence interval (CI). The null hypothesis of the Mantel-Haenszel test is that the common difference in response rates is zero. The family-wise two-sided type I error level $\alpha = 0.05$ will be controlled by a hierarchical test procedure based on two-sided tests with $\alpha = 0.05$ as described in [Section 12.4.7.4](#).

CCI

CCI

CCI

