12.4.7.4 Multiple comparisons/multiplicity

The family-wise two-sided type I error level $\alpha = 0.05$ for comparisons of treatment groups U and P on the primary and key secondary endpoints will be controlled by a hierarchical test procedure based on two-sided tests with $\alpha = 0.05$.

The hierarchical procedure for primary analysis (Section 12.4.1.1) will be performed as described below. First, using the Mantel-Haenszel test of the null hypothesis that the common difference in response rates at Day 30 is zero, Group U versus Group P will be tested for superiority for proportion of GFL-responders, second for proportion of HFL-responders, and third for proportion of LCL-responders. The test procedure will stop once statistical significance could not be reached.

In case statistical significance can be established for all three primary efficacy endpoints, the procedure will proceed to key secondary endpoints (Section 12.4.1.2.1): As next steps, Mantel-Haenszel tests for superiority of Group U versus Group P will be conducted for proportion of subjects with a score of 0 (no) or 1 (mild) on MAS at maximum contraction as assessed by the *investigator* at Day 30 for GFL, then HFL and finally LCL anatomical region. Thereafter, Mantel-Haenszel tests for superiority of Group U versus Group P will be conducted for proportion of subjects with a score of 0 (no) or 1 (mild) on MAS at maximum contraction as assessed by the *subject* at Day 30 for GFL, then HFL and finally LCL anatomical region.

Finally, GAIS as assessed by the subject at Day 30 of MP will be tested as described in Section 12.4.1.2.1.

The hierarchical test procedure will stop once statistical significance could not be reached.

For any other statistical tests on primary or key secondary endpoints (e.g. comparison of treatment groups G&F and P), no type I error adjustment will be performed. The same accounts for any statistical analyses of further secondary and other endpoints.

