The OLEX period will comprise two additional treatment cycles, Cycle 2 and Cycle 3 with durations of 120 days each plus up to 30 days for eligibility reassessments per cycle. During each cycle, eligible subjects will receive simultaneous injections of NT 201 at a total dose of 64 U in all three facial areas. Eligibility criteria will be evaluated before reinjection.

The primary objective of this study is to assess the efficacy of simultaneous intramuscular injections of NT 201 in subjects with moderate to severe UFL in comparison to placebo.

The secondary objectives are to assess efficacy and safety of simultaneous single and repeat-dose intramuscular injections of NT 201 in subjects with moderate to severe UFL.

3 Determination of Sample Size

Overall, 360 subjects are planned to be randomized to three treatment groups (UFL, GFL&HFL or Placebo) with a randomization of 2:1:1 at baseline visit V2.

The FDA required that the clinical development program includes at least 300 completed subjects who are treated simultaneously in all three anatomical areas (GFL, HFL, LCL) under placebo-controlled conditions to support safety. Since two pivotal studies are planned for demonstration of NT 201 efficacy and safety in the combined GFL, HFL and LCL treatment and assuming that up to 15% of the subjects will not complete the study, 180 subjects will be randomized per study to be treated in all three anatomical areas (Group U). A randomization ratio of 2:1:1 for the treatment groups in this study results in 90 subjects for Groups G&H and P respectively.

These sample sizes provide sufficient power also to assess efficacy under conservative assumptions. For proportions of 20% LCL-responders in Group U and 5% in Group P, a power of 93% is achieved for one-sided Fisher's exact test at $\alpha = 2.5\%$. Moreover, if proportions of HFL- and GFL-responders of at least 40% for Group U and at most 5% for Group P are assumed, the samples sizes provide power close to 100%.

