6.1.2.1 Key Secondary Efficacy Endpoints and Key Secondary Efficacy Estimands

[figure not shown]
Main estimators for key secondary estimands will be calculated for the target population of main key secondary estimands and ICEs will be handled as described in [Section 6.4.6](#).

Main estimators for main key secondary dichotomous MAS-based efficacy estimands ([Section 5.1.2](#)) correspond to main estimators for main primary estimands (see [Section 6.1.1.1](#)). Missing data will be imputed as described in [Section 6.1.1.1](#). For all three anatomical regions and for investigator's as well as subject's assessments on the MAS, stratum-adjusted differences in proportions for overall comparisons of treatment Group U versus Group P (reference) with corresponding 95% Mantel Haenszel CIs and Mantel-Haenszel test p-values will be calculated. Responder rates with two-sided 95% Wilson CIs will be provided as well.

Main estimator for the main key secondary estimand based on subject's GAIS (see [CCI](#)) will be analysis of covariance with factors treatment group and site, and mean of baseline MAS for HFL, GFL, and LCL at maximum contraction assessed by subject as covariate.

CCI

CCI

According to the definition of the key secondary estimand based on subject's GAIS CCI specific ICEs will be handled by applying the composite strategy. In these cases, missing subject's GAIS ratings or ratings of CCI (see Section 6.4.6 on ICEs), regardless of whether the GAIS score from subject assessment at Day 30 (V4) is available or whether it is missing for the respective subject.

Least squares (LS) means, standard error, and two-sided 95% CI per treatment group and LS mean treatment difference ("Group U" – "Group P") with associated two-sided 95% CI and t-Test p-value will be provided. The null hypothesis of this t-Test is that the LS mean treatment difference is zero.

A similar SAS code to the following statements will be employed for this analysis:

[figure not shown]
CCI

The resulting value will be rounded to two decimals.

Multiplicity adjustment strategy for comparisons of treatment groups U and P on key secondary endpoints is described in Section 6.4.3.

CCI

CCI

Results for Group G&H from any analyses will only be interpreted descriptively.

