6.4.3 Multiple Comparisons/Multiplicity

The family-wise two-sided type I error level $\alpha = 0.05$ for comparisons of treatment groups U and P on the primary and key secondary endpoints will be controlled by a hierarchical test procedure based on two-sided tests with $\alpha = 0.05$.

The hierarchical procedure for primary analysis ([Section 6.1.1.1](#)) will be performed as described below. First, using the Mantel-Haenszel test of the null hypothesis that the common difference in response rates at Day 30 is zero, Group U versus Group P will be tested for superiority for proportion of GFL-responders, second for proportion of HFL-responders, and third for proportion of LCL-responders. The test procedure will stop once statistical significance could not be reached.

In case statistical significance can be established for all three primary efficacy endpoints, the procedure will proceed to key secondary endpoints ([Section 6.1.2.1](#)): As next steps, Mantel-Haenszel tests for superiority of Group U versus Group P will be conducted for proportion of subjects with a score of 0 (no) or 1 (mild) on MAS at maximum contraction as assessed by the *investigator* at Day 30 for GFL, then HFL and finally LCL anatomical region. Thereafter, Mantel-Haenszel tests for superiority of Group U versus Group P will be conducted for proportion of subjects with a score of 0 (no) or 1 (mild) on MAS at maximum contraction as assessed by the *subject* at Day 30 for GFL, then HFL and finally LCL anatomical region.

Finally, GAIS as assessed by the subject at Day 30 of MP will be tested as described in [Section 6.1.2.1](#).

The hierarchical test procedure will stop once statistical significance could not be reached.

For any other statistical tests on primary or key secondary endpoints (e.g. comparison of treatment groups G&H and P), no type I error adjustment will be performed. The same accounts for any statistical analyses of further secondary and other endpoints.

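### If the confirmatory p-value is the Mantel-Haenszel risk difference over its Sato standard error, its two-sided size at the planned 5% placebo rate is about 6.1% to 6.3%, slightly above the stated 0.05; a site-stratified null-variance test avoids this

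*SAP*

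**What the plan says.** SAP 6.1.1.1, like protocol 12.4.1.1, defines the primary comparison of Group U with Group P: "Mantel-Haenszel stratum weights and the Sato variance estimator will be used to calculate the stratum-adjusted risk difference, with study site serving as stratum variable". In every region the resulting difference "will be provided with two-sided p-value and 95% Mantel-Haenszel confidence interval (CI". The null hypothesis is put on the same quantity. Protocol 12.4.1.1 has "The null hypothesis of the Mantel-Haenszel test is that the common difference in response rates is zero", and the synopsis speaks of "Mantel-Haenszel tests of the null hypothesis that the stratum-adjusted difference in response rates at Day 30 is zero".

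The multiplicity sections use the same label: protocol 12.4.7.4 tests in fixed order "using the Mantel-Haenszel test of the null hypothesis that the common difference in response rates at Day 30 is zero". The responder-type key secondary endpoints follow suit in SAP 6.1.2.1, "with corresponding 95% Mantel Haenszel CIs and Mantel-Haenszel test p-values will be calculated". SAP 6.4.3 says that the family-wise two-sided 0.05 level "will be controlled by a hierarchical test procedure based on two-sided tests with" a level of 0.05 each.

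Sato is the only variance that the readable text names. SAP 6.1.1.1 announces program code for this analysis, but the public copy does not show it.

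**The concern.** Two tests fit this wording. One divides the adjusted risk difference by its Sato standard error. The other is the CMH test, whose variance is computed under the null. They give different p-values when responders are few.

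The Sato variance uses the observed rates, so a chance low placebo count shrinks it and inflates the statistic. With 2:1 allocation the smaller arm is placebo, so the error leans towards NT 201. A fixed sequence holds 0.05 only if every test in it does. At the planned rates for glabellar frown lines (GFL) and horizontal forehead lines (HFL), the procedure almost always reaches LCL. The size of the LCL test is then the family-wise error.

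**Working it through.** **Inputs.** 180 and 90 subjects (SAP 3). LCL planned at 20% versus 5%; GFL and HFL at 40% or more versus 5% or less (SAP 3). About 10 sites (protocol synopsis), none pooled (SAP 6.4.5). All Group U and Group P subjects are kept by imputation (SAP 6.1.1.1). Assumption: 10 equal sites of 18 and 9, varied below.

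**The plan's own figure.** SAP 3: "For proportions of 20% LCL-responders in Group U and 5% in Group P, a power of 93% is achieved", for a one-sided Fisher's exact test at 2.5%. Exact enumeration at 180 versus 90 gives 93.5%, so the figure is reproduced. Fisher's test is not the analysis test, so this figure says nothing about the size of the confirmatory p-value.

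**Formulas.** In site h, let x1, x2 be the responders, n1, n2 the arm sizes, n = n1 + n2 and w = n1·n2/n.
- Risk difference: d = Σ[(x1·n2 − x2·n1)/n] / Σw.
- Sato variance: (d·ΣP + ΣQ)/(Σw)², with P = [n1²·x2 − n2²·x1 + n1·n2·(n2 − n1)/2]/n² and Q = [x1(n2 − x2) + x2(n1 − x1)]/(2n).
- CMH: the numerator Σ(x1 − n1·m/n), with m = x1 + x2, is divided by the square root of Σ n1·n2·m(n − m)/[n²(n − 1)], without continuity correction.

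Either test rejects when |z| ≥ 1.96. With one stratum, the Sato variance equals the ordinary unpooled variance.

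**One example, single stratum: 13/180 versus 2/90.**
- d = 0.0722 − 0.0222 = 0.05; w = 180·90/270 = 60.
- Sato: P = −10.556, Q = 2.737; variance = (2.737 − 0.528)/3600 = 0.000614; z = 2.02; p = 0.044.
- CMH: pooled rate 15/270 = 0.0556; variance on the difference scale = 0.0556·0.9444·(1/180 + 1/90)·270/269 = 0.000878; z = 1.69; p = 0.091.

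Group U responders needed for p < 0.05, Sato against CMH: 9 against 12 with 1 placebo responder, 13 against 16 with 2, 17 against 19 with 3, 23 against 25 with 5.

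**Size at 5% in both arms.** Exact, one stratum: Sato 6.29% (5.01% favouring NT 201, 1.28% against); CMH 4.56% (1.82% and 2.74%). Simulation with 1,000,000 trials per layout gives a Sato size of 6.26% (5 sites), 6.12% (10 sites), 6.04% (15 sites), 6.14% (10 uneven sites) and 6.15% (10 sites with rates from 1% to 9%). With one stratum, 97% of the false rejections favouring NT 201 come from trials with at most 2 placebo responders, which are 17% of trials.

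**Other null rates, 10 equal sites (%):**

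| Common rate | Sato two-sided | Sato, favouring NT 201 | CMH two-sided | CMH, favouring NT 201 |
|---|---|---|---|---|
| 1 | 4.6 | 4.3 | 4.2 | 0.02 |
| 2 | 9.0 | 8.1 | 3.8 | 0.5 |
| 3 | 7.7 | 6.6 | 4.2 | 1.3 |
| 5 | 6.1 | 4.8 | 4.6 | 1.8 |
| 10 | 5.5 | 3.8 | 4.9 | 2.0 |
| 20 | 5.4 | 3.2 | 5.0 | 2.3 |

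At 1% there is no two-sided excess, but the tail favouring NT 201 is still above 2.5%.

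**Fixed sequence.** With GFL and HFL at 40% versus 5% and LCL null at 5% (300,000 trials), LCL is reached in 100.0% of trials. Family-wise error is 6.2% with Sato (4.9% favouring NT 201) and 4.7% with CMH (1.9%).

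**At the planned effects.** LCL at 20% versus 5%: power is 97.0% with Sato and 95.2% with CMH, and the two p-values disagree in 1.8% of trials. At 40% versus 5% both powers are near 100% and the p-values do not disagree. Coverage of the Sato 95% interval is 94.7% at 20% versus 5% and 94.8% at 40% versus 5%.

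**The case against.** The strongest reply is that the deciding text is not in front of us. The SAP announces code for exactly this analysis, and the plan repeatedly says Mantel-Haenszel test, which may well mean CMH. A reader might infer that the plan fails to control its type I error, or that it leaves the variance undefined. The documents support neither inference. An excess is shown only under the Sato reading, and the unseen code may already use a null variance.

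A second reply is that, on the Sato reading, the method is fully specified and standard, which leaves only a finite-sample criticism of about 1.2 points. That is a fair description of the size, but it does not remove the mismatch with a stated 0.05, or the near-doubling of the tail that leads to a superiority claim.

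A third is that CMH is no free improvement. It is conservative in the superiority tail, and its opposite tail is above 2.5% (2.7% at a 5% rate, 4.2% at 1%), although two-sided size stays at or below 5%. It also gives up the automatic agreement of test and interval. This stands, and it is why an equivalent stratified score test is acceptable as well.

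Three further inferences go too far. The 7.7% and 9.0% sizes belong to placebo rates that no section predicts for LCL. No size can be given for the key secondary tests, because the plan states no placebo rate for them. And the Sato interval covers well at the planned rates, so it needs no replacement.

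**Conclusion.** The point holds conditionally. If the p-value uses the Sato standard error, as the prose most naturally reads, two-sided size is about 6.1% to 6.3% at 180 versus 90 and a 5% rate in both arms, with 4.8% to 5.0% favouring NT 201. The family-wise error then slightly exceeds 0.05 when LCL is null and GFL and HFL work as planned. If the p-value comes from CMH, size is about 4.6% and nothing is wrong beyond wording.

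The result rests on the planned arm sizes and placebo rate, and changes little over 1 to 15 sites, uneven sites and site-to-site variation in rates. At the planned effects the choice would alter the LCL result in about 1.8% of trials. Severity is minor.

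**What to change.** Keep the Mantel-Haenszel risk difference and its Sato 95% interval for estimation. In SAP 6.1.1.1, 6.1.2.1 and 6.4.3, and in protocol 12.4.1.1, 12.4.1.2.1 and 12.4.7.4, state three things for the responder endpoints on the Merz Aesthetics Scales:
- The confirmatory two-sided p-value comes from a site-stratified null-variance test: CMH without continuity correction, or an equivalent stratified score test.
- The Sato variance serves the interval only.
- The p-value decides if the two disagree.

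If the code already does this, saying so in the text is enough.

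The cost is one sentence per section and at most a software option. With CMH, LCL power falls from 97.0% to 95.2% at 20% versus 5% (above the stated 93%), and from 80% to 72% if the true LCL rates were 15% versus 5%, a scenario assumed here. CMH is conservative for superiority at low rates (1.8% against a nominal 2.5% at a 5% rate). P-value and interval can disagree near the boundary: 1.8% of trials at 20% versus 5%, and 8% at 15% versus 5%. A stratified score interval that matches the test would reduce this and is optional.
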